1.0 Research Introduction

1.1 Purpose/Specific Aims

The goal of the study is to determine whether a high-dose corticosteroid regimen in patients admitted to the hospital with COPD exacerbations is associated with better clinical outcomes and at acceptable risk of adverse effects compared to a low-dose corticosteroid regimen. The study population includes patients ≥ 40 years-old with a ≥ 10 pack-years smoking history and a diagnosis of COPD, emphysema, or chronic bronchitis who present to the emergency room with increased dyspnea, increased sputum, or increased cough that requires admission to the hospital. We will perform a prospective, randomized, double-blinded study to determine if a high-dose corticosteroid regimen, which is already in use in clinical practice, decreases treatment failure compared to a low-dose corticosteroid regimen that is based on national consensus guidelines.

A. Objectives

Primary Aim: To determine if a high-dose corticosteroid regimen is associated with decreased rates of treatment failure compared to a low-dose corticosteroid regimen.

Secondary Aims:

- a) To determine if a high-dose corticosteroid regimen is associated with a reduced length of stay.
- b) To determine if a high-dose corticosteroid regimen is associated with better quality of life scores.

Tertiary Aim: To determine if a high-dose corticosteroid regimen is associated with an increased risk of short-term adverse effects.

B. Hypotheses / Research Question(s)

Protocol Number:

PI Name: [name]

Protocol Title: Determining Optimal Dose of
Corticosteroids in COPD Exacerbations: A
Pilot Study

3

RESERVED FOR IRB STAMP
DO NOT MODIFY THIS SPACE

IRB Form Version v120116

Our hypothesis is that high-dose corticosteroids are associated with a decreased rate of treatment failure, shorter length of hospital stay, and improved quality of life with similar risk of adverse effects.

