- ii. Secondary Outcomes: Length of hospital stay and quality of life measured by Clinical COPD Questionnaire. The CCQ consists of 10 questions about the severity of COPD symptoms and limitation of activities over the prior week.
- iii. Tertiary Outcome: Composite outcome of short-term adverse effects. Defined as hyperglycemia, hypertension, adrenal suppression, psychiatric disturbance, infection, and gastrointestinal bleed that require a consultation, an invasive procedure, or initiation of a specific therapy.

Protocol Number:

PI Name: [name]

Protocol Title: Determining Optimal Dose of
Corticosteroids in COPD Exacerbations: A
Pilot Study

5

RESERVED FOR IRB STAMP
DO NOT MODIFY THIS SPACE

IRB Form Version v120116

Subject participation in the study ends after the 30 day follow up period. Study staff will also maintain contact with the patient's hospital physician and actively review the patient's chart during the index hospitalization for safety and adverse effect monitoring. Please see the study data collection form for additional specific data points that will be collected.

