1.6 Study Variables

A. Independent Variables, Interventions, or Predictor Variables

Our independent variable is the corticosteroid intervention. We chose to compare two commonly used corticosteroid regimens for COPD exacerbation that vary by dosage strength but not duration. Both of these regimens may be considered "standard of care."

B. Dependent Variables or Outcome Measures

- i. Primary Outcome: The composite of treatment failure defined as death, intubation, re-admission for COPD exacerbation, or intensification of therapy (increased steroid use, change of antibiotic therapy) within a 30-day follow-up period.
- ii. Secondary Outcomes: Length of hospital stay and quality of life measured by Clinical COPD Questionnaire. The CCQ consists of 10 questions about the severity of COPD symptoms and limitation of activities over the prior week.
- iii. Tertiary Outcome: Composite outcome of short-term adverse effects. Defined as hyperglycemia, hypertension, adrenal suppression, psychiatric disturbance, infection, and gastrointestinal bleed that require a consultation, an invasive procedure, or initiation of a specific therapy.

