4.9 Risks to Subjects

A. Description of Subject Risk

Patients entered into this study would have received corticosteroids regardless of study participation. The optimal dose of corticosteroids in the treatment of COPD exacerbations in patients admitted to the hospital is unknown. The proposed regimen for the low-dose

Protocol Number:

12

PI Name: [name]

Protocol Title: Determining Optimal Dose of
 Corticosteroids in COPD Exacerbations: A
 Pilot Study

*RESERVED FOR IRB STAMP
 DO NOT MODIFY THIS SPACE*

IRB Form Version v120116

corticosteroid group is based on national consensus guidelines, and the regimen for the high-dose group, on current clinical practices. Thus, the risks to subjects from study participation are comparable to current standard of care. Any patient who does not clinically improve appropriately can have their regimen intensified based on the clinical judgement of his/her physician. Additionally, if the treating physician feels that the patient is experiencing undue adverse effects from study corticosteroid, the patient may be withdrawn from the study at any time. Minor side effects (ie. hyperglycemia) from short-term systemic corticosteroids are common and generally limited in duration to the duration of treatment. They are an accepted consequence of the standard of care for COPD exacerbation. Major adverse effects are uncommon.

B. Procedures for Risks to Embryo, Fetus, and/or Pregnant Subjects

N/A, these subjects are excluded from the study.

C. Risks to Non-Subjects

N/A

D. Assessment of Social Behavior Considerations

Temporary psychiatric symptoms or exacerbation of pre-existing psychiatric disease are uncommon but potential side effects of corticosteroid therapy. The duration of these side effects are limited to the duration of corticosteroid therapy. Patients entered into this study would have received corticosteroids regardless of study participation. Thus, study participation is unlikely to increase risk of these side effects.

▪ **Reasonably Foreseeable Risks**

There are no other reasonably foreseeable social behavior risks of participation in this study.

▪ **Risk Of Imposing An Intervention On Subject With Existing Condition**

See above.

▪ **Other Foreseeable Risks**

N/A

▪ **Observation And Sensitive Information**

N/A

E. Minimizing Risks

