6.0 Research Data Protection and Reporting

6.1 Data Management and Confidentiality

A. Descriptive statistics (e.g., means, standard deviations, ranges, frequency distributions) will be examined for all relevant measures, and transformations of measures will be considered on the bases of distribution diagnostics and outlier analysis. The baseline characteristics of the patients in each of the two arms of the trial will be described and compared using chi-square statistics for categorical variables and t-tests or Wilcoxon statistics for continuous variables.

Protocol Number:

PI Name: [name]

Protocol Title: Determining Optimal Dose of
Corticosteroids in COPD Exacerbations: A
Pilot Study

15

RESERVED FOR IRB STAMP
DO NOT MODIFY THIS SPACE

IRB Form Version v120116

The intention-to-treat principle will be used for all randomized comparisons of study outcomes. The event rates for the primary, secondary, and tertiary clinical outcomes will be compared according to assigned corticosteroid group using chi-square statistics. The test for differences between groups in the composite primary outcome will be conducted at an alpha level of 0.05. The event rates for the individual clinical events and the additional pre-specified clinical events will be tested by treatment group with an alpha=0.01 to adjust for multiple comparisons. Event rates, absolute differences, and relative risks will be estimated, and 95% confidence intervals will be calculated.

B. This is a pilot study to establish an adequate sample size for a larger scale study as well as baseline event rates, thus a power analysis is not included in this submission.

C. Paper data will be stored in a locked filing cabinet in the Department of General Internal Medicine. A password-protected electronic database (that does not contain patient identifiers) will be stored on a HIPAA-compliant university computer at the same location. [name] will have sole access to this data until the study enters the data analysis phase. All study personnel are already trained in HIPAA procedures and have signed HIPAA confidentiality agreements as part of obtaining access to the Sunrise Clinical Manager system.

D. Collected data will be reviewed for quality and internal consistency by study staff after initial collection and before the data analysis phase of the study.

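### The only pooled harm outcome counts treated hyperglycemia together with less common major harms, so neither a near-null nor a raised result can be read as evidence about acceptable or similar risk

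*Combined protocol and SAP*

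**What the plan says.** Sections 1.3(iii) and 1.6(B.iii) define a single pooled harm outcome ("Tertiary Outcome: Composite outcome of short-term adverse effects"). Its components are given as "Defined as hyperglycemia, hypertension, adrenal suppression, psychiatric disturbance, infection, and gastrointestinal bleed that require a consultation", and one threshold applies to all six: they count if they are events "that require a consultation, an invasive procedure, or initiation of a specific therapy". There is no grading or weighting, and no other pooled harm outcome.

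Section 4.9.A says "Minor side effects (ie. hyperglycemia) from short-term systemic corticosteroids are common", treats such effects as an accepted part of standard care, and adds "Major adverse effects are uncommon". It gives no rates, and Section 1.4 says that there are no preliminary data.

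Section 1.1 hypothesises "improved quality of life with similar risk of adverse effects". No margin or decision rule for similarity is given.

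Section 6.1.A compares the tertiary outcome by chi-square without stating its alpha. It adds: "The event rates for the individual clinical events and the additional pre-specified clinical events will be tested by treatment group with an alpha=0.01". It also promises rates, absolute differences and relative risks with 95% confidence intervals, but does not say whether the individual events include the six adverse-effect components.

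**The concern.** Harm is half of the study's stated goal, which is better outcomes at an acceptable level of adverse effects. The one pooled measure of harm puts an effect that the protocol already accepts beside effects that could make the high-dose regimen unacceptable. A patient counted for newly treated hyperglycemia adds nothing to the composite if a gastrointestinal bleed or psychiatric disturbance follows.

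Two misreadings become possible. If the common component is frequent and similar in both arms, a real excess of major harm is diluted and the composite looks close to null. If hyperglycemia rises with dose, the composite rises too, and a reader cannot tell from it whether major harm rose. The plan has no level of summary between all six effects together and one sparse event at a time. The pilot is also meant to supply outcome rates for sizing a larger trial, and a composite rate made up mostly of minor events is a poor basis for planning that trial's safety outcome.

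**Working it through.** **Inputs from the documents.** 125 subjects in total (Sections 1.5 and 4.5); chi-square test; alpha 0.01 for individual events (Section 6.1.A). The plan states no event rate, effect size or power, so there is no figure of its own to reproduce.

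**Assumptions.** 1:1 allocation (62 low dose, 63 high dose), no dropout, two-sided uncorrected chi-square with power by exact binomial enumeration. Major effects (adrenal suppression, psychiatric disturbance, infection, gastrointestinal bleed, pooled): 5% low v 15% high. Common part *h* (treated hyperglycemia or hypertension): equal in both arms and independent of major effects. This grouping is for illustration; the protocol itself names only hyperglycemia as minor.

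**Formula.** Composite rate = 1 − (1 − h)(1 − m), where m is the major-effect rate. For h = 30%:
- low: 1 − 0.70 × 0.95 = 33.5%
- high: 1 − 0.70 × 0.85 = 40.5%
- standard error = √(0.335 × 0.665/62 + 0.405 × 0.595/63) = 8.6 points, so the 95% half-width is about 17 points.

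| Common part h | Low v high | Difference (points) | Relative risk | Power at 0.05 |
|---|---|---|---|---|
| 0 (major effects alone) | 5.0% v 15.0% | 10 | 3.0 | 46% |
| 10% | 14.5% v 23.5% | 9 | 1.62 | 25% |
| 20% | 24.0% v 32.0% | 8 | 1.33 | 17% |
| 30% | 33.5% v 40.5% | 7 | 1.21 | 13% |
| 50% | 52.5% v 57.5% | 5 | 1.10 | 8.5% |

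**Share of composite events with no major effect, h = 30%.** Low: 0.30 × 0.95/0.335 = 85%. High: 0.30 × 0.85/0.405 = 63%.

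**If the common part rises with dose.** Start from 30% in the low-dose arm.
- Common part up 1.25-fold, major effects unchanged at 5%: high-dose composite = 1 − 0.625 × 0.95 = 40.6%. This is practically the 40.5% produced by a tripling of major effects with no change in the common part.
- Both rise (1.25-fold and 5% v 15%): 1 − 0.625 × 0.85 = 46.9%, power 33%. Each change alone accounts for about 7 points.
- Both rise (1.5-fold and 5% v 15%): 1 − 0.55 × 0.85 = 53.2%, power 60%. The common part alone would give 1 − 0.55 × 0.95 = 47.8%, a rise of 14.3 points against 7.0 for major effects alone.

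**Single-component tests.** If the four major effects are equally frequent and independent, each has 1 − 0.95^(1/4) = 1.3% v 1 − 0.85^(1/4) = 4.0%, or about 0.8 v 2.5 expected events. Power at alpha 0.01 is about 0.6%.

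**Limit of separation.** Major effects alone need 141 per arm for 80% power at 5% v 15%, and 376 per arm at 2% v 6%. At 2% v 6% the present sample gives 19% power.

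**The case against.** The strongest reply is that the treatment threshold already acts as a severity filter. Section 4.9.A speaks of hyperglycemia in general, not of hyperglycemia that needs a consultation, procedure or new therapy, and the plan gives no rate for the latter. This stands: the claim that hyperglycemia will supply most composite events is conditional, and at a 10% common part the dilution is moderate.

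Second, a reader might infer that a diluted composite would lead the trial to conclude similar risk, so that the design favours its hypothesis. The documents do not support that. No rule turns non-significance into similarity. Confidence intervals will be reported, and a half-width of about 17 points would not show similarity. Sections 1.5 and 6.3.F disclaim power. If hyperglycemia rises with dose, the composite moves against the hypothesis, so the direction is not fixed.

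Third, Section 6.1.A plans individual-event rates with intervals. If these cover the adverse-effect components, a later bleed would appear in its own row and the information is not lost. That answers part of the concern, but the coverage is not stated and single rows would be very sparse.

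Fourth, low power comes mostly from the sample size, and the division into major and minor is a judgement. Both stand. They argue for a descriptive addition that follows the protocol's own wording.

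**Conclusion.** The point holds as one of interpretation. The only pooled harm outcome cannot distinguish a modest rise in an accepted effect from a tripling of major harm: under the assumptions above the two give 40.6% and 40.5% in the high-dose arm. With major effects at 5% v 15% and an equal common part of about 30% or more, the relative risk falls from 3.0 to 1.21 or less and power from 46% to 13% or less. With a 10% common part the figures are 1.62 and 25%. All of these rates, the independence and the equal common part are assumptions; the plan supplies none.

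The composite could therefore be misread in either direction. It would be too strong to say that a large excess of major harm would necessarily be hidden. This is a worthwhile, inexpensive improvement to a tertiary outcome in a declared pilot.

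**What to change.** In Sections 1.3(iii), 1.6(B.iii) and 6.1.A:
- Keep the six-item composite.
- Add a pre-specified descriptive composite, with the same threshold, that excludes hyperglycemia, the one component the protocol itself names as minor. Add a sensitivity version that also excludes hypertension.
- State that each of the six components is reported by arm with its rate, absolute difference, relative risk and 95% confidence interval.
- State that any conclusion on similar or acceptable risk rests on both composites and their intervals, and that a non-significant difference is not evidence of similarity.

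The cost is protocol wording and a few table rows. Section 6.3.B indicates that predefined adverse effects are already on the data collection form. There are drawbacks. Events will be few, intervals wide, and there is one more comparison to label as descriptive. The new composite may itself be dominated by treated infection. While hypertension stays in, some dilution remains: if treated hypertension ran at 10% in both arms, the 10% row of the table would apply. The change does not make 125 patients adequate for testing harm.

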1.3 Research Design and Methods

We will perform a pilot study evaluating two commonly used doses of corticosteroids in the treatment of acute exacerbation of COPD. The study design is a randomized, double-blinded, prospective interventional trial. Our research staff will recruit, consent, and enroll patients admitted to the hospital with a diagnosis of COPD exacerbation. We will create randomization tables that will be provided to the research pharmacist. The research pharmacist will be telephoned, and they will randomly assign the patient to a low-dose or high-dose corticosteroid regimen. Medication will be prepared by a research pharmacist to maintain blinding. For in-hospital intravenous medication, the research pharmacist will provide to the nurses a container with the patient's name and medication without the dose. For oral medication, the pills will be inserted into a capsule and provided to nurses for in-hospital administration. At the time of discharge, a container filled with the remaining oral medication will be provided to the patient. Subjects receiving intravenous corticosteroid may be discharged to a nursing home before completion of the IV component of the regimen. Their regimen will be converted to oral equivalents, and a container will be provided to the nursing home. Copies of the patient brochure, signed consent, and written discharge instructions will also be provided. All data will be collected by our research staff via chart review of index and subsequent hospitalizations within the 30-day follow up period, as well as a phone interview with the patient at 30-days. The Clinical COPD Questionnaire will be administered during the phone interview. A patient is considered lost to follow-up if the data collection is not collected within 14 days after the 30-day follow-up date. In the event that we are unable to contact the patient, we will telephone the participant's personal medical doctor to confirm the patient's status. If necessary, we will obtain medical records for any outpatient physician visits made during the 30-day follow up period.

- i. Primary Outcome: The composite of treatment failure defined as death, intubation, re-admission for COPD exacerbation, or intensification of therapy (increased steroid use, change of antibiotic therapy) within a 30-day follow-up period.

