1.9 Interviews, Focus Groups, or Surveys

A. Administration

The Clinical COPD Questionnaire (CCQ) will be administered by research staff during a telephone interview at 30 days following subject enrollment into the study. The patient will be provided this document in advance, at the time of hospital discharge, for reference.

B. Study Instruments

The CCQ is a validated tool utilized in prior literature to assess quality of life in patients with COPD. Higher scores indicate increased severity of symptoms and/or poorer quality of life, and are associated with increased mortality. ^{17, 18, 19, 20, 21}

In addition to the CCQ, research staff will query the patient about study endpoints during the follow-up telephone interview (re-admission, changes to steroid regimen, antibiotic therapy, and steroid-associated adverse effects that require a consultation, an invasive procedure, or initiation of a specific therapy).

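### A listed steroid effect managed only by withdrawal from study corticosteroid is scored as no event in the tertiary harm composite, and no other outcome or table counts it

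*Combined protocol and SAP*

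**What the plan says.** Section 1.3 defines the tertiary outcome as a composite of hyperglycemia, hypertension, adrenal suppression, psychiatric disturbance, "infection, and gastrointestinal bleed that require a consultation, an invasive procedure, or initiation of a specific therapy". Section 1.6 repeats the definition. Section 1.9 carries the same threshold into the 30-day telephone interview, which asks about re-admission, "changes to steroid regimen, antibiotic therapy, and steroid-associated adverse effects that require a consultation, an invasive procedure, or initiation of a specific therapy".

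Section 4.9 says that if the treating physician feels the patient is "experiencing undue adverse effects from study corticosteroid, the patient may be withdrawn from the study at any time". Withdrawal does not appear among the qualifying actions in Sections 1.3, 1.6 or 1.9.

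The primary composite does not pick it up either. Its treatment component is "intensification of therapy (increased steroid use, change of antibiotic therapy) within a 30-day follow-up period", so only an increase in steroid counts.

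On harm, the tertiary aim in Section 1.1 is "To determine if a high-dose corticosteroid regimen is associated with an increased risk of short-term adverse effects", while the hypothesis in the same section expects "improved quality of life with similar risk of adverse effects". Section 6.1 plans comparisons by assigned group under intention-to-treat, with event rates, absolute differences, relative risks and 95% confidence intervals.

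**The concern.** The composite measures severity by what was done about the effect, and it leaves out one response that the protocol itself provides. A patient whose psychiatric disturbance or hyperglycemia was judged bad enough for withdrawal, and who needed nothing else, is scored the same as a patient with no adverse effect. A milder case given one new drug is scored as an event.

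Management by withdrawal alone is plausible on the protocol's own account. Section 4.9 describes minor effects such as hyperglycemia, and also psychiatric effects, as generally lasting no longer than the steroid treatment. Both are components of the composite.

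At stake is the harm side of the comparison. The study aims to show benefit at acceptable risk, and Section 1.5 says that the pilot exists to establish outcome rates for a larger trial. An adverse-effect rate that omits these cases would carry over into that design.

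**Working it through.** **Step 1: what each place counts.** The plan states no adverse-effect or withdrawal rate, so there is no figure to reproduce. The first check is textual.

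| Place | Is withdrawal for an adverse effect counted? |
|---|---|
| Tertiary outcome, 1.3 and 1.6 | No. Three triggers only |
| Interview, 1.9 | Regimen changes are asked about, but adverse effects keep the three triggers |
| Primary outcome, 1.3 and 1.6 | No. Increased steroid use only |
| Statistical plan, 6.1 | Compares the outcomes as defined; no table of withdrawals |
| Safety monitoring, 6.3 | Case-by-case review; cumulative data not reviewed; safety tests marked not applicable |

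The missed group is therefore patients with a listed effect, withdrawn for it, with no consultation, procedure or new specific therapy.

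**Step 2: direction.** Let pL and pH be the true adverse-effect rates, and fL and fH the share of each arm's events managed by withdrawal alone.

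- Reported difference = pH(1 − fH) − pL(1 − fL) = (pH − pL) − (pH·fH − pL·fL)
- Reported relative risk = (pH/pL) × (1 − fH)/(1 − fL)

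The difference shrinks when pH·fH exceeds pL·fL and grows when it is smaller. The relative risk changes only if the two shares differ.

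**Step 3: numbers.** All rates and shares are assumptions.

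| True rates, low v high | fL, fH | Reported rates | Difference (points) | Relative risk |
|---|---|---|---|---|
| 15% v 30% | 0, 0 | 15.0% v 30.0% | 15.0 | 2.00 |
| 15% v 30% | 20%, 20% | 12.0% v 24.0% | 12.0 | 2.00 |
| 15% v 30% | 10%, 30% | 13.5% v 21.0% | 7.5 | 1.56 |
| 15% v 30% | 30%, 10% | 10.5% v 27.0% | 16.5 | 2.57 |
| 10% v 20% | 0, 0 | 10.0% v 20.0% | 10.0 | 2.00 |
| 10% v 20% | 20%, 20% | 8.0% v 16.0% | 8.0 | 2.00 |
| 10% v 20% | 10%, 30% | 9.0% v 14.0% | 5.0 | 1.56 |
| 10% v 20% | 30%, 10% | 7.0% v 18.0% | 11.0 | 2.57 |

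When the true high-dose rate is twice the low-dose rate, the difference is unchanged at fL = 2·fH. It is overstated only beyond that point.

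**Step 4: the same in patients.** Section 1.5 gives 125 subjects. The allocation ratio is not stated, so I assume 62 low-dose and 63 high-dose. Suppose the composite as defined counts 10 and 15 events: 15/63 − 10/62 = 7.7 points, relative risk 1.48.

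| Missed, low / high | Difference if counted | Relative risk if counted | Change in difference |
|---|---|---|---|
| 0 / 3 | 18/63 − 10/62 = 12.4 | 1.77 | +4.8 |
| 1 / 5 | 20/63 − 11/62 = 14.0 | 1.79 | +6.3 |
| 3 / 3 | 18/63 − 13/62 = 7.6 | 1.36 | −0.1 |
| 4 / 1 | 16/63 − 14/62 = 2.8 | 1.12 | −4.9 |

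For scale, the 95% half-width around 7.7 points is 1.96 × √(0.161×0.839/62 + 0.238×0.762/63) = 1.96 × 0.071 = 13.9 points.

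**The case against.** The strongest reply is that requiring a consultation, a procedure or a new therapy is a coherent threshold that can be verified in the chart. A physician's decision to withdraw a patient is more subjective, and redefining the composite is a matter of preference. That stands as a reason to leave the main definition alone. It does not explain why withdrawals for adverse effects should go untabulated.

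Second, safety data are collected daily in hospital and again at 30 days (Section 6.3), the interview asks about regimen changes, and the data collection form is not among the documents. The form may already record withdrawals and their reasons. This is a fair limit on any claim about what is collected. It does not alter what the outcome counts.

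Third, any shift illustrated above is well inside the sampling error, the outcome is tertiary, and Sections 1.5 and 6.3 disclaim power. All of this is true, and it lowers the priority.

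Three stronger readings are tempting but lack support.

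- A reader might infer that all intolerance leading to withdrawal goes uncounted. Only cases managed by withdrawal alone are missed, and nothing in Section 4.9 says that withdrawal replaces consultation or therapy.
- A reader might infer that the comparison is necessarily pulled toward similar risk. No passage gives withdrawal rates by arm, and Steps 3 and 4 show that the difference can shrink, stay put or grow.
- A reader might infer that withdrawal shortens steroid exposure and so prevents later events. Section 4.9 speaks of withdrawal from the study, and says that these patients would have received corticosteroids anyway. Steroid treatment may therefore continue outside the trial.

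**Conclusion.** The gap in the definition is established by the text: a listed effect whose only management was withdrawal from study corticosteroid is scored as no event, and no other outcome or planned comparison counts it. Withdrawn patients who also met a trigger are counted provided their data are kept. The available text does not say whether withdrawn patients are followed to day 30, although Section 6.1 promises intention-to-treat.

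The size is unknown. The absolute difference is understated if high dose truly causes more adverse effects and withdrawal-only cases form an equal or larger share of high-dose events. It can be overstated if their share is sufficiently larger in the low-dose arm. The relative risk is unchanged when the shares are equal. In the patient-count illustrations, counting these cases moves the difference by between −4.9 and +6.3 points. That range reflects the chosen assumptions and is not an estimate. If no patient is managed this way, nothing changes.

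The consequence is confined to the tertiary harm estimate and its use in planning the larger trial. The primary result is not touched. Optional to moderate priority.

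**What to change.** In Section 6.1, pre-specify a table by assigned group of patients withdrawn from study corticosteroid because of an adverse effect, naming the effect, with the risk difference and its 95% confidence interval. Keep the tertiary composite as defined, and add a sensitivity analysis in which withdrawal from study corticosteroid because of the listed effect is a further qualifying action. State alongside whether withdrawn patients remain in follow-up to day 30, so that the denominators are clear.

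The cost is a few sentences, one table and at most one field on the data collection form, which may already hold it. The daily safety review and the interview question on regimen changes largely supply the data. The downside is an item that rests on physician judgement; blinding limits the bias from this, and confining the item to a sensitivity analysis leaves the defined outcome intact. Nothing changes in how patients are treated or when they are withdrawn.
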